4.5 Antibiotics Therapy Arm

Patients in the antibiotics arm will receive a total of 10 days of antibiotics, with a minimum of 24 hours using an IV antibiotic formulation (administered in q8, q12, or q24 hour regimens with or without concurrent oral antibiotics) followed by oral antibiotics for the remainder of the 10 days. Patients will be offered a treatment regimen of antibiotics based on guidelines published jointly by the Surgical Infection Society and the Infectious Disease Society of America. 19 The first dose of antibiotics will be given in the ED at the time of diagnosis of appendicitis for both treatment arms. This flexibility in antibiotics choice is not expected to impact outcome but should improve the generalizability of the results, and therefore, implementation of the findings. Any of the IV antibiotics options (Single antibiotic-Cefoxitin, Ertapenem, Moxifloxicin, Tigecycline, Ticarcillin-Clavulanic Acid or Dual antibiotics-Metronidazole or Clindamycin plus one of the following-Cefazolin, Cefuroxime, Ceftriaxone, Cefotaxime, Ciprofloxacin, Levofloxacin) will be considered acceptable. At many sites, these will be administered to inpatients only. For clinicians and patients interested in outpatient receipt of antibiotics, the available options will include Ertapenem or Moxifloxacin (q24) alone or Ceftriaxone (IV) plus IV or oral Metronidazole or Clindamycin, as tolerated. Although these antibiotics are considered acceptable and equally efficacious for intra-abdominal infections by the aforementioned professional societies, outcomes based on antibiotics used and antibiotics regimen will be monitored at regular intervals by the DCC and reported to the Data and Safety Monitoring Board (DSMB) for consideration in protocol modification. After IV antibiotics are administered for a period of at least 24 hours, a regimen of oral antibiotics will be continued to complete a total treatment length of 10 days. Acceptable oral regimens should be based on in vitro activity against aerobic and anaerobic Gram-negative bacteria known to cause appendicitis, and practical experience with oral antibiotic regimens used to treat diverticulitis. Preferred oral antibiotic regimens include Moxifloxacin alone, and combinations such as Metronidazole or Clindamycin, for anaerobic bacteria coverage, plus Ciprofloxacin or Levofloxacin, or an oral Cephalosporin for aerobic Gram-negative bacteria coverage. Antibiotics will be prescribed by clinicians and procured by patient as per usual clinical care.

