4.6 Appendectomy Arm

All patients randomized to appendectomy will receive one dose of antibiotics per currently accepted standards described in Section 4.5 when diagnosis is confirmed in the ED. Patients may also receive preoperative antibiotics per hospital standards for surgical infection prevention bundle.

Appendectomy will be performed by an open or laparoscopic approach, depending on patient and surgeon preference.

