- 4. Subgroup Monitoring As an important clinical subgroup of interest, the DSMB will actively monitor patients with appendicolith on safety, PROs, and the rate of treatment by appendectomy among those randomized to receive antibiotics. No formal stopping rules are proposed based upon results observed within the appendicolith subgroup because patient advisors determined that information for this substantial group of patients would be informative to decision makers even if only a small proportion (<25%) had successful treatment with antibiotics. Another clinical subgroup of interest includes patients treated with different antibiotic types and/or regimens and specifically those who received completely outpatient versus at least some inpatient antibiotic therapy. The DSMB will actively monitor patients based on antibiotics received and whether or not they ultimately had surgery. Subgroup monitoring will focus on safety, PROs, and the rate of eventual appendectomy. No formal stopping rules are proposed based on results observed within the antibiotic type and regimen subgroups since patient advisors determined that information for this group of patients would be informative to decision makers.

- 5. Revisions These monitoring guidelines may be revised at the discretion and recommendation of the DSMB.
- 6. DSMB Recommendations After each interim review of the data, the DSMB will recommend one of the following actions:
 - a. Continuation of the study as is;
 - b. Continuation of the study with protocol changes in the interest of safety or study accrual;
 - c. Discontinue the study due to inadequate patient accrual, follow-up, or study conduct;
 - d. Discontinue the study due to patient safety in the antibiotics arm; and
 - e. Discontinue the study for futility, low conditional power for the primary question of interest.
- 6. Shell DSMB report tables are located in Appendix A.

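### The DSMB subgroups for antibiotic setting and regimen are defined by therapy received, with no time point; read literally, the comparison is biased in favour of outpatient care

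*Protocol*

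**What the plan says.** Protocol section 8.6, item 4 (Subgroup Monitoring), names antibiotic type and regimen as a subgroup of interest, "specifically those who received completely outpatient versus at least some inpatient antibiotic therapy". It continues: "The DSMB will actively monitor patients based on antibiotics received and whether or not they ultimately had surgery". The outcomes follow: "Subgroup monitoring will focus on safety, PROs, and the rate of eventual appendectomy". It then adds: "No formal stopping rules are proposed based on results observed within the antibiotic type and regimen subgroups".

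Section 4.5 describes how setting is chosen: "At many sites, these will be administered to inpatients only. For clinicians and patients interested in outpatient receipt of antibiotics, the available options will include" a short list of regimens. Setting is therefore a matter of site, clinician and patient preference and is not randomized. The same section has the DCC track results by drug and regimen over time; these are to be "reported to the Data and Safety Monitoring Board (DSMB) for consideration in protocol modification".

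No section of the protocol fixes the group at the index visit, by intended setting or within a time window. The final SAP does not define this subgroup; its list of additional exploratory subgroups covers age, sex, comorbidity and insurance. Section 8.6 refers to shell DSMB tables in Appendix A, which are not in the text available for this review.

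**The concern.** The definition is one-way. A single hospital antibiotic treatment takes a patient out of the wholly outpatient group, and nothing can bring that patient back. The usual trigger for the move, return to hospital with worsening or recurrent disease, lies on the path to appendectomy, which is one of the outcomes compared. The split therefore conditions on a consequence of failure. Regimen type has the same weakness if a switch after a poor response changes the antibiotics counted as received. Membership can also change between the six-monthly DSMB reports, because section 4.5.2 allows a second antibiotic course for recurrence after four weeks.

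The protocol recognises the problem elsewhere: section 8.3 warns that a naive as-treated analysis is biased because patients treated successfully with antibiotics may differ from the rest. The monitoring split carries no such safeguard.

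At stake is what the DSMB concludes about the less supervised setting. A real disadvantage of outpatient treatment could be hidden, or inpatient treatment could appear to carry an excess of failures, when the board considers changes to the protocol.

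**Working it through.** The documents give no rate, sample size or alpha for this comparison, so there is no figure of the plan's own to reproduce. The check is reclassification arithmetic.

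**Inputs**
- Grouping rule and outcomes: Protocol 8.6, item 4, read literally.
- *f*, the true appendectomy rate, the same in both settings: 15% and 20% are assumptions for four weeks. 25% corresponds to the Background section's statement that nearly three in four antibiotic-treated patients in earlier trials avoided surgery in the first year.
- *s*, the share starting as outpatients: assumed. The documents give no figure.
- *k*, the fraction of failing outpatients who receive antibiotics in hospital and so change group: assumed.

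**Formulas**
- Apparent outpatient rate = *f*(1 − *k*) / (1 − *fk*)
- Apparent inpatient rate = [(1 − *s*)*f* + *sfk*] / [(1 − *s*) + *sfk*]

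**Worked case**, *f* = 0.15, *s* = 0.40, *k* = 0.50:
- Outpatient: 0.075 / 0.925 = 8.1%
- Inpatient: (0.09 + 0.03) / (0.60 + 0.03) = 0.12 / 0.63 = 19.0%

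**Range**

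| *f* | *s* | *k* | Outpatient | Inpatient |
|---|---|---|---|---|
| 15% | 40% | 50% | 8.1% | 19.0% |
| 15% | 40% | 80% | 0.03/0.88 = 3.4% | 0.138/0.648 = 21.3% |
| 15% | 40% | 100% | 0% | 0.15/0.66 = 22.7% |
| 20% | 40% | 80% | 0.04/0.84 = 4.8% | 0.184/0.664 = 27.7% |
| 15% | 10% | 80% | 3.4% | 0.147/0.912 = 16.1% |
| 25% | 30% | 25% | 0.1875/0.9375 = 20.0% | 0.19375/0.71875 = 27.0% |
| 25% | 30% | 50% | 0.125/0.875 = 14.3% | 0.2125/0.7375 = 28.8% |

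**Direction.** For any *k* above zero, (1 − *k*)/(1 − *fk*) is below 1, so the outpatient rate is understated. The inpatient rate becomes a weighted average of *f* and 1, so it is overstated. The formulas move only outpatients who go on to appendectomy. If a fraction *j* of the other outpatients also receives hospital antibiotics, the direction is unchanged as long as *k* exceeds *j*, that is, as long as failing patients are the more likely to be treated in hospital.

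**Possible reversal.** Suppose outpatient care is truly worse, 35% v 25%, with *s* = 30% and *k* = 50%. Outpatient: 0.175/0.825 = 21.2%. Inpatient: (0.175 + 0.0525)/(0.70 + 0.0525) = 30.2%. The order is reversed. At *k* = 25% it is 28.8% v 27.7%, so most of the true difference is hidden.

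**After the fix.** With groups fixed at first disposition, *k* = 0 and both formulas return *f*: equal true rates show as equal for every *s*.

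**The case against.** The strongest reply is that the literal reading is not the only one. The Rationale (section 2.1) and section 4.5 present outpatient treatment as a way of delivering the initial course, and the Antibiotics Form in section 5.3 separates inpatient from discharge antibiotics. The subgroup may therefore mean the initial schedule, and the shell tables may derive it that way. If so, no patient changes group. This stands as far as it goes: a reader might infer that the DSMB tables are certain to show a false outpatient advantage, and the documents do not establish that. They do leave the rule unwritten, and the wording used points to treatment received.

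A reader might also infer that nearly every outpatient who needs rescue surgery is reclassified through surgical prophylaxis. The only sentence on this, "Patients may also receive preoperative antibiotics per hospital standards for surgical infection prevention bundle", is in section 4.6, covers patients randomized to appendectomy, and is permissive. Whether a perioperative dose counts as inpatient antibiotic therapy is not defined, so values of *k* near 100% have no documentary support.

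For safety, a reader might assume that each such admission is also an SAE. Sections 6.2.1 and 9.2 exempt some hospitalizations for appendicitis, in different words, so the effect on SAE rates is uncertain. The effect on PROs was not calculated.

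Section 4.5 limits many sites to inpatient administration, so the outpatient share may be small. At *s* = 10% the inpatient rate barely moves (16.1% against a true 15%), although the outpatient rate is still 3.4%.

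Finally, the formal safety tests compare the ITT arms, the DSMB also sees the arm-wide appendectomy rate, and this subgroup has no stopping rule. All of that is correct and limits the consequences.

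**Conclusion.** The point holds as a defect of definition. Setting and regimen are classified by treatment received, with no time point, and are set against an outcome that can itself cause the classification to change. On the literal reading, the bias in eventual appendectomy favours outpatient care for any reclassification above zero, provided that failing outpatients are the more likely to be treated in hospital. Its size cannot be taken from the documents. With a true 15% in both settings and 40% starting as outpatients, it ranges from 8.1% v 19.0% (half reclassified) to 3.4% v 21.3% (80% reclassified). Safety and PROs would be affected to an uncertain degree.

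The comparison is descriptive and the primary ITT analysis of EQ-5D is not affected. The point is still worth correcting, because regimen outcomes go to the DSMB as possible grounds for changing the protocol. A reader might also conclude that any breakdown by eventual surgery must be removed. That goes too far: such a table can usefully describe patients who had surgery after antibiotics, provided that it is not used to compare regimens.

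**What to change.** In section 8.6, item 4, and in the DSMB table derivations:

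- Classify setting and regimen at the first disposition from the index visit: discharged on an outpatient schedule v admitted, and first regimen prescribed.
- Keep each patient in that group whatever happens later.
- Report later admission, regimen switch and appendectomy as outcomes.
- Label the comparison non-randomized, and show site and appendicolith status beside it.
- Mark any table split by eventual surgery as descriptive only.

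If the DCC already classifies by index-visit setting, one sentence saying so settles the main question.

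The cost is a change of wording and of a table derivation. The ED Visit Form (admission and discharge times) and the Antibiotics Form (inpatient and discharge antibiotics) in section 5.3 already collect what is needed, and no clinical rule changes. There are two drawbacks: the initial-plan groups will include some patients whose setting later changed, and confounding by who is offered outpatient care remains.

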9.0 Study Related SAEs

9.1 Identification of SAEs

Participants in the randomization and observational cohorts will be monitored for SAEs throughout their study surveillance period (enrollment through the optional extended follow-up). The occurrence of an SAE may come to the attention of study personnel during study follow-up

phone interview, by UW study staff personnel conducting follow-up, or by a study participant calling the study team or presenting for medical care. If an SAE comes to the attention of study personnel via patient or family report, the site research coordinator will be notified that an SAE form needs to be completed. The site research coordinator will then use the EMR to fill out the SAE form. The site PI will then complete the form and sign the form. The SAE form will then be submitted to the DCC who will provide it to the ISM. The ISM will review the SAE form and ask the surgical site lead for additional clarification or specification as he/she sees necessary. SAE forms for events other than death will be summarized for the DSMB every 6 months; however, deaths due to any cause will be reported to the DSMB immediately.

9.2 SAE Reporting

Life-threatening complications or SAEs are a very rare possibility with surgical treatment and even less likely with antibiotic treatment. SAEs are defined as one of the following conditions (also listed in section 6.2.1):

- 1. Death during the period of protocol-defined surveillance;
- 2. Life-threatening event related to the treatment or significant disability/incapacity related to the treatment; or
- 3. Inpatient hospitalization (other than for treatment of recurrent appendicitis).

All SAEs will be:

- 1. Recorded on the appropriate SAE case report form;
- 2. Adjudicated by the ISM;
- 3. Reviewed and evaluated by the DSMB;
- 4. Followed until satisfactory resolution or until the study investigators deem the event to be chronic or the participant to be stable;
- 5. Reported to the study investigators, the project managers, and site IRBs per their reporting guidelines; and
- 6. The study investigators will also report SAEs to PCORI in its role as funder.

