6.2 Secondary Outcomes

6.2.1 Clinical Complications

Death, SAEs, and complications (reported as AEs via EMR review) will be assessed and recorded through the study surveillance period. Complications (reported as AEs) will incorporate NSQIP standards and definitions as well as events related to antibiotic-related complications.

Serious Adverse Events	Adverse event
Death	
Life-threatening event	
Severe antibiotic reaction	Mild/moderate antibiotic reaction
CVA or stroke	
MI requiring treatment or cardiac arrest	Myocardial infarction Atrial arrhythmia
Unplanned admit to ICU	
Acute Renal Failure (requiring dialysis)	Major UTI (e.g., pyelonephritis) Urinary retention Acute Renal Failure (no dialysis) Progressive renal insufficiency
C. difficile colitis (requiring colon resection)	
Pulmonary embolism requiring therapy	DVT/PE requiring treatment
Coma >24 hours	
Septic shock (requiring pressors)	Sepsis
Serious Adverse Events (continued)	Adverse event (continued)
Bleeding requiring transfusion	
Newly infected prosthetic graft infection	
(such as a cardiac valve that gets infected or	
synthetic bypass graft infection secondary to	
appendicitis)	
Mechanical ventilation >48 hours	Tracheal reintubation/tracheostomy
Colostomy or ileostomy	NG tube replacement (non-routine)
	Bowel obstruction
	Ileus
	Organ/space infection (including peritonitis)
	Surgical site infection
	Intra-ab Abscess
	Severe dehydration
	Hernia
	Malignant hyperthermia
	Pneumonia
	Other infection
	Other post-op occurrence: unspecified
	Other non-operative intervention: unspecified
	Unplanned (re)operative intervention during index
Other life threatening count	C. difficile colitis (not requiring colon resect)
Other life threatening event	
Rehospitalization (other than for txt of appendicitis)	

Monitored event
Appendiceal cancer
Perforation
Length of stay postoperatively

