1. Safety Monitoring – We will perform interim analyses of accruing safety data. SAEs (described in section 9.1) will be monitored throughout the course of the study. The DSMB will review tabulated SAEs by treatment group every six months; however, all deaths will be reported to the DSMB immediately. With additional guidance from the DSMB, we propose to monitor and compare three safety endpoints between randomization groups: 1) per-patient indicator of "any" SAE, 2) per-patient SAE count, and 3) all-cause mortality. The research coordinators at each practice site will monitor participants for, or be alerted by UW study staff regarding the presence of, SAEs and AEs during inpatient stays using EMR. This process includes reviews of SAEs and AEs that occur at other hospitals not included in the study, with details obtained through requested records from those hospitalizations. An adjudication process related to these events will be led by a clinician not otherwise involved in the trial. This independent safety monitor (ISM) will review SAE forms for data quality control. SAE forms needing additional specification will be returned to the site PI for completion prior to finalization. All SAEs will also be adjudicated by the surgical site lead.

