9.3 Assignment of SAEs as Treatment Related

The determination of whether an SAE is related to the treatment will be assessed by the ISM and surgical site lead, based on supporting documentation provided by the research coordinators case reports or in consultation with the treating physician, as needed.

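### Protocol 9.2 and 6.2.1 define SAEs differently and 8.6 does not say which list feeds the safety stopping rule, so the count tested can depend on a relatedness judgement

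*Protocol*

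**What the plan says.** Protocol 9.2 introduces its definition with "SAEs are defined as one of the following conditions (also listed in section 6.2.1" and gives three conditions. The first is "Death during the period of protocol-defined surveillance". The second is "Life-threatening event related to the treatment or significant disability/incapacity related to the treatment; or". The third is "Inpatient hospitalization (other than for treatment of recurrent appendicitis". Only the second carries a relatedness condition.

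Protocol 6.2.1 has a two-column table of SAEs and AEs. Its SAE column names life-threatening events twice. It also names specific events, among them stroke, unplanned ICU admission, "Bleeding requiring transfusion", a stoma and ventilation beyond 48 hours, with no condition on cause. Pulmonary embolism needing therapy is in the SAE column, while "DVT/PE requiring treatment" is in the AE column.

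Protocol 8.6 monitors three safety endpoints: whether a patient has any SAE, the number of SAEs per patient, and death from any cause. They are compared one-sided at P<0.011 under a Pocock boundary. For the SAEs themselves it says: "SAEs (described in section 9.1) will be monitored throughout the course of the study". Section 9.1 explains how SAEs come to light and are reported; it does not define them.

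On causality, 9.3 says: "The determination of whether an SAE is related to the treatment will be assessed by the ISM and surgical site lead". Section 8.1 states that the trial is unblinded.

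**The concern.** Two of the three monitored endpoints are built from SAEs, and a site completing a form must decide which list applies. The same non-fatal event in the index stay can be an SAE under 6.2.1 and not under 9.2. Where 9.2 is followed, whether a life-threatening or disabling event enters the count depends on a causality judgement, made by people who are not stated to be blinded to the arm.

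Section 8.6 focuses interim monitoring on the first four weeks, which include the index stay, where the lists differ most. What is at stake is whether the safety comparison shown to the DSMB means the same thing at every site and in both arms. The final SAP also lists serious adverse events among the Aim 2 clinical endpoints without defining them, so the ambiguity carries into that comparison.

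**Working it through.** **1. The two lists side by side**

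| Event | Section 9.2 | Section 6.2.1, SAE column |
|---|---|---|
| Death | Counts, any cause | Counts |
| Non-fatal life-threatening event | Only if related to treatment | Listed, no relatedness condition |
| Disability or incapacity | Only if significant and related | Not listed |
| Unplanned ICU admission, transfused bleeding, stoma, ventilation beyond 48 hours | Only through the second or third condition | Listed outright |
| Hospital admission | Inpatient stay, exempting recurrent appendicitis | Re-admission, exempting treatment of appendicitis |
| Treated pulmonary embolism | Only through the second or third condition | SAE column and AE column |

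The admission rows differ in two ways. Read literally, 9.2 does not clearly leave out the index admission, whereas 6.2.1 speaks of re-admission. Also, a participant treated wholly as an outpatient (allowed in 4.5) and later admitted for the same unresolved episode is exempt under 6.2.1 but not clearly exempt under 9.2.

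**2. What the relatedness condition can remove**

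Deaths enter 9.2 whatever the cause, and so do new admissions not exempted. What remains is non-fatal life-threatening or disabling events without a qualifying new admission, chiefly in the index stay. This reads the third condition as a new admission; otherwise almost every admitted participant would have an SAE.

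**3. The plan's own threshold**

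Inputs from 8.5 and 8.6: overall one-sided alpha 0.025; interim analyses at 400 and 800–1000 randomized; a final analysis at 1552; so three looks. The Pocock constant c solves P(Z1<c, Z2<c, Z3<c) = 0.975, with corr(Zi, Zj) = √(ti/tj) for i<j.

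- Equally spaced looks (t = 1/3, 2/3, 1): c = 2.2895 and nominal p = 1 − Φ(c) = 0.01103. The stated 0.011 is reproduced; its overall alpha is 0.02495.
- Two equally spaced looks would give 0.01469, so 0.011 belongs to a three-look plan.
- With information proportional to enrollment and looks at 400, then 800 to 1000, then 1552, a constant 0.011 gives overall alpha 0.0259 to 0.0263. This is a small departure, separate from the point here.

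**4. Sensitivity of the result to one patient**

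The test is the one-sided Fisher's exact test named in 8.6, with equal arms. For a antibiotics-arm and b appendectomy-arm patients with an SAE, and n per arm:

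p = Σ (k = a to a+b) C(n,k)·C(n, a+b−k) / C(2n, a+b)

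At the first look n = 400/2 = 200. The documents give no SAE rate, so a and b are assumed.

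| Antibiotics vs appendectomy | p | Below 0.011? |
|---|---|---|
| 15 vs 4 | 0.0083 | Yes |
| 14 vs 4 | 0.0136 | No |
| 15 vs 5 | 0.0182 | No |

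Dropping one antibiotics-arm patient as unrelated takes 15 vs 4 to 14 vs 4 and removes a crossing. Dropping one appendectomy-arm patient takes 15 vs 5 to 15 vs 4 and creates one.

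The smallest crossing splits at 200 per arm are 7 vs 0, 9 vs 1, 11 vs 2, 15 vs 4 and 24 vs 10. The check covered appendectomy counts of 0, 1, 2, 4, 6, 8, 10, 15 and 20 at 200, 450 and 776 per arm. In every case, at the smallest crossing count, one fewer antibiotics patient or one more appendectomy patient brings p back above 0.011.

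**The case against.** The case for leaving the text alone has substance. An independent safety monitor, a clinician not otherwise involved in the trial, leads adjudication and reviews every SAE form. Stopping is at the discretion of the DSMB and faculty statistician, the DSMB sees tabulated SAEs every six months, and it may revise the guidelines. Relationship to treatment is already a recorded field (10.0). Section 8.6 says SAEs are described in 9.1, not defined there, so the wrong pointer is editorial. Section 6.2.1 is itself not wholly free of cause: it includes severe antibiotic reaction and a graft infection secondary to appendicitis. All of this stands and limits the harm. None of it says which list feeds the two SAE endpoints, and the surgical site lead, who also judges relatedness, is not independent of the trial.

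Four stronger readings are tempting and are not supported:

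- *The stopping boundary itself moves.* It does not. It is fixed at P<0.011; only the count and its p value change.
- *Section 9.3 is circular.* It is not. Deaths and qualifying hospitalizations are SAEs without a relatedness test, so 9.3 has work to do on events already classed as SAEs.
- *The relatedness condition systematically removes surgical events and tilts the comparison against antibiotics.* The documents do not show this. Index-stay surgical events are the ones most readily judged related (12.0 names bleeding as a risk of surgery), so the condition would tend to keep them. They would drop out if judged neither life-threatening nor disabling, and nothing gives their frequency by arm.
- *The trigger falls by a known amount.* At 450 per arm the crossing count is 21 against 8 appendectomy patients and 15 against 4. Reading that as the effect of the 9.2 wording assumes four lost events and holds the other arm fixed. The documents support neither step.

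**Conclusion.** The concern holds in limited form. The protocol says its two SAE definitions match and they do not, and 8.6 does not choose between them. Where 9.2 is followed as written, a relatedness judgement in an open trial, by assessors not stated to be blinded, decides whether some non-fatal events are counted, chiefly those in the index stay. All-cause mortality, deaths and admissions that qualify under both wordings are unaffected, and the P<0.011 threshold is sound for three equally spaced looks.

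The size is one patient: near the threshold, one reclassification changes which side of 0.011 the result falls on, and it can work in either direction. This assumes that the event is that patient's only SAE and that the counts are close to the threshold. How often that would happen, and which arm it would favor, cannot be derived from the documents. The correction should be made, but the stopping rule is not invalid without it.

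**What to change.** Use one SAE definition in 6.2.1, 8.6 and 9.2, and state in 8.6 that the monitored endpoints count every such event regardless of causality. Specifically:

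- remove relatedness as an entry condition from both parts of the second condition in 9.2;
- add significant disability or incapacity to the SAE column of 6.2.1;
- reconcile the two hospitalization wordings, including whether the index admission is covered and which appendicitis admissions are exempt;
- place treated pulmonary embolism in one column;
- change the 8.6 cross-reference from 9.1 to 9.2;
- keep relatedness (9.3) as the separate attribute that 10.0 already records.

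The cost is wording changes and a re-check of records. Filed SAE forms alone are not enough, because the events at issue may never have been filed as SAEs; the Adverse Events Forms and EMR abstractions in 5.3 must be searched too. No new data item is needed. Slightly more events will be counted, some of them unrelated to treatment.
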